9. ANALYTIC PLAN

EXPOSURES: **Primary:** 1) SDB defined by AHI, i.e. number of apneas + hypopneas/hour of sleep. **Secondary:** 1) Hypoxia: % sleep time with $\text{SaO}_2 < 90\%$, 2) Obstructive Sleep Apnea [obstructive apneas and hypopneas/hour of sleep, obstructive apnea hypopnea index (OAH)], 3) Central Sleep Apnea [central apneas/hour of sleep, Central Apnea Index (CAI)], 4) Periodic Breathing and 5) EEG arousals [per hour of sleep, Arousal Index (AI)].

OUTCOME: 1) PAF (SA1) and 2) AF burden defined as frequency of AF paroxysms overall and based on self-reported sleep vs. wake (SA2 and 3)

COVARIATES: Age, race, body mass index (BMI, kg/m^2), waist circumference (cm), anti-arrhythmic/beta blocker/calcium channel blocker/ACE inhibitor/angiotensin receptor blocker medications, pacemaker, defibrillator, heart failure (NYHA class), BP, diabetes mellitus, left atrial volume, LVEF, caffeine use, alcohol use and smoking (current versus never smoker or pack years) and activity level. When assessing hypoxia as the relevant exposure, pulmonary disorders will be included as potential confounders.

Table 2. Mediator (SA1) or Outcome (SA3)

Domain	Primary	Secondary	Rationale
Echocardiographic Measures	Left Atrial Volume (ml/m^2)	LA Pressure, LA Systolic Strain, RA area, RA Pressure, LAA Peak Anterograde Flow Velocity (cm/s), Right Atrial Pressure (mmHg), LVEF, LVMI, LVH (concentric $\text{LVMI} > 0.41$, eccentric ≤ 0.41).	Left Atrial Volume predicts risk of AF and PAF ¹⁰³⁻¹⁰⁶ . Secondary measures also associated with AF.
Autonomic Function (Heart Rate Variability)	SDNN (ms) (Time Domain HRV Measure)	Time Domain (r-MSSD (ms), pNN50), Frequency Domain [LF (Hz), HF (Hz), LF/HF]], Graphical Parameters (HR patterns, power spectral analysis, Poincaré plots and beat-by-beat HR tachograms) and Novel non-linear measures (e.g. Conditional Entropy ¹⁰⁷).	Reduced SDNN and LF/HF have been identified as AF triggers ⁴⁰ .
Systemic	hs-CRP (mg/L)	IL-6 (pg/ml), sIL-6R (ng/mL)	hs-CRP and IL-6 associated with SDB and AF ⁴⁷⁻⁴⁹ . s-IL6R varies with overnight

Inflammation			hypoxia ⁴⁶
Oxidative Stress	Endothelin-1 (pg/ml)	Urinary isoprostane 8-epi-prostaglandin F2a (ng/mmolCr), Oxidized LDL (U/L)	Endothelin-1 implicated in AF ⁵⁷⁻⁵⁹ . Isoprostane ⁶⁰⁻⁶² and oxidized LDL sensitive to SDB ⁷⁶ .

ANALYTIC METHOD BY AIM.

SA1. Quantify the extent that SDB and its subtypes are associated with PAF. This aim will be addressed by fitting conditional logistic regression models that condition on the matched pair. We will separately analyze each SDB variable (primary variable: AHI) to obtain an estimate and 95% CI of the odds ratio of PAF for a 1-unit increase in the SDB exposure. Non-linear effects between SDB and the log odds of PAF will be assessed using restricted cubic splines. Knots for the spline will be based on the SDB threshold at which PAF risk increases. Unadjusted and hierarchical adjusted models will be performed using the covariates listed above.

The secondary exposure variables (e.g. hypoxia, OAHI, CAI, AI) will be considered in separate models.

Exploratory Aim 1a. Cardiac structure, autonomic and biochemical variables (Table 2) will explain a proportion of the SDB and PAF relationship. This aim will be addressed by applying Pearl's mediation formula¹⁰⁸ to the conditional logistical regression model. This approach will allow a causally sound definition of the mediation effect of a given intermediate variable in the relationship between SDB (defined by AHI) and PAF. The approach involves a model for each mediator (e.g. a general linear model for a continuous mediator) and possibly a random effect to account for clustering due to matching and can be thought of as a generalized structural equations model. This approach will allow us to simultaneously assess multiple mediators and will also allow us to consider AHI as a continuous variable. Each model will be fit using likelihood methods and model fit will be checked using appropriate information criteria. After fitting the overall model, we will obtain, for each mediator, an estimate of the indirect effect (e.g. the portion of the overall effect of SDB on PAF mediated through the intermediate variable). A bootstrap resampling technique will be used to obtain a 95% CI for each indirect effect. If the CI does not contain zero, this will indicate statistically significant mediation.

Exploratory Aim 1b. Explore age interactions in the SDB-PAF relationship. Each conditional logistic regression model will include an interaction between age and SDB to investigate if age is a modifier of the effect of SDB on PAF, i.e. whether the odds ratio of PAF for a 1-unit increase in SDB varies by age.

SA2. Examine patterns of PAF burden via 1-week continuous ECG monitoring relative to SDB. We will model the relationship between mean frequency AF paroxysm variation and SDB (e.g. AHI considered as a continuous variable). A linear regression model will be used to assess possible quadratic and threshold effects of SDB on variation. These models may also include sleep state by SDB interaction terms (along with the state indicator) to examine if the effect of SDB on variation differs by sleep state. Maximum likelihood (based on a normal distribution for variation if appropriate) will be used to fit models, and the Akaike Information Criterion (AIC) will be used to select the best fitting model. Estimates of the effect of SDB on variation (and corresponding 95% CI) will be obtained based on the selected model.

SA3. Examine the effects of SDB (AHI \geq 15) treatment for 3 months on AF paroxysm frequency and also measures of autonomic function, cardiac morphology, biochemical measures in those with SDB and PAF. For this subgroup of SDB (AHI \geq 15) and PAF, we will perform paired t-tests to compare pre- and post- treatment mean outcomes (Primary outcome: AF paroxysm frequency from 1-week ECG monitoring) and also ECHO and biochemical measures. For any outcome for which a departure in normality is found (based on the Shapiro-Wilk test) but a transformation of the outcome cannot be found to adequately address the issue,

we will use the Wilcoxon signed rank sum test to detect a difference in the distribution of the pre- and post- responses. This assessment is not intended to be confirmatory, but rather to provide estimates of variability and effect sizes to inform future studies/randomized trials. Linear regression models will then be developed to model PAF burden at the 3 month visit by conditioning on baseline PAF burden, baseline SDB, and time from baseline to 3 month visit. Additional adjusted models will carefully consider the covariates list above.

POWER BY AIM.

SA1. A sample size of 300 will be able to detect an odds ratio of 1.50 with 80% power (and 1.60 with 90% power), assuming a 2-sided alpha level of 0.05, a correlation in AHI between cases and controls of zero and a probability of PAF of 0.20 when AHI is set at its mean value. Note that the odds ratio is interpreted as the odds ratio for PAF for a 1 standard deviation increase in AHI. Alternatively assuming that the probability that $AHI \geq 15$ for patients without PAF is 30%⁶⁴, a sample size of 150 matched pairs will be able to detect an odds ratio of PAF of 2.13 with 90% power assuming a 2-sided alpha-level of 0.05. Note that this calculation assumes that the correlation for SDB between subjects with and without PAF is 0.20, as suggested by Dupont (1988)¹⁰⁹ when the correlation is unknown. Our prior cross-sectional work demonstrating SDB-AF odds ratio point estimates of 2-4^{1,2} supports sufficient power to address this aim.

Exploratory Sub-Aim 1a. To calculate the power to detect mediation, a difference in coefficients approach will be used¹¹⁰ which involves the fitting of two logistic regression models that model the association between SDB ($AHI \geq 15$) and the log odds of PAF (one with and the other without the potential mediator in the model) to estimate the proportion of exposure effect that is mediated. Assuming a correlation between the adjusted and unadjusted effect estimates of 0.9 and that the probability of PAF in SDB and no SDB is 0.07 and 0.01 respectively (based upon prior data²), a sample size of 150/group will be able to detect mediation proportions of 0.5 with 84% power assuming a 2-sided 0.05 alpha-level test. Although power may be reduced depending on the observed imbalance in sample sizes for the SDB and no SDB groups, power will be increased due to matching (not taken into account here to be conservative).

SA2. Using a two-sample t-test (2-sided 0.05 alpha-level) to test for a difference in mean variation between the SDB ($AHI \geq 15$) and no SDB groups, a sample size of 150 (75 with SDB and 75 without SDB) will detect mean differences within 0.46 standard deviations with 80% power and 0.53 standard deviations with 90% power.

SA3. For a log-normally distributed outcome, assuming a correlation between pre- and post-PAF burden of 0.8 and a coefficient of variation of 1.5 (based upon prior data¹¹¹), a sample size of 75 will detect a mean ratio between post and pre PAF burden of 0.83 with 83.1% power based on a paired t-test and a two-sided significance level of 0.05.

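### SA1 power for AHI ≥ 15 is overstated: on the plan's own inputs, 150 matched pairs give about 80% power at an odds ratio of 2.13, not 90%

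*Combined protocol and SAP*

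**What the plan says.** The SA1 paragraph under Power by Aim in Section 9 (Analytic Plan) is repeated in Section 10 (Data Analysis). It makes two power statements.

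- **Continuous AHI.** A sample of 300 detects an odds ratio per standard deviation of 1.50 with 80% power, or 1.60 with 90%. This assumes zero case-control correlation and "a probability of PAF of 0.20 when AHI is set at its mean value".
- **AHI ≥ 15, offered as an alternative.** "a sample size of 150 matched pairs will be able to detect an odds ratio of PAF of 2.13 with 90% power", at two-sided alpha 0.05, with 30% of patients without PAF exposed. The plan adds that "this calculation assumes that the correlation for SDB between subjects with and without PAF is 0.20".

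The paragraph closes by saying that the group's earlier odds ratios of 2 to 4 "supports sufficient power to address this aim". The SA1 analysis itself is described as "fitting conditional logistic regression models that condition on the matched pair".

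**The concern.** The second statement gives every input that a matched-pair power calculation needs, so it can be checked directly, and it does not check. The stated type II error at an odds ratio of 2.13 is 10%; the actual one is about 20%. SA1 is the first of the listed aims, and this is one of only two power statements for it. A reader who trusts the 90% could read too much into a null result for AHI ≥ 15. The sentence on sufficient power also rests on it, and the low end of the effect range cited there falls below the usual 80%.

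**Working it through.** **Inputs, all from the SA1 paragraphs.** n = 150 pairs; odds ratio ψ = 2.13; exposure in controls p0 = 0.30; exposure correlation φ = 0.20; two-sided alpha 0.05 (z = 1.96). The planned model conditions on the pair, so ψ is the within-pair odds ratio, the ratio of the two discordant-pair probabilities.

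**Formulas.** With p1 the exposure prevalence in cases:

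- P11 = p1·p0 + φ·√[p1(1−p1)·p0(1−p0)]
- discordant probability t = p1 + p0 − 2·P11
- π = ψ/(1+ψ)
- power = Φ{ [√(n·t)·(π − 0.5) − 1.96·0.5] / √[π(1−π)] }

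At ψ = 2.13, π = 0.6805, π − 0.5 = 0.1805 and √[π(1−π)] = 0.4663.

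**Form A: p1 solved so that the within-pair odds ratio is exactly 2.13.**

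- p1 = 0.439, P11 = 0.177
- discordant probabilities 0.262 and 0.123 (ratio 2.13), so t = 0.3846 and n·t = 57.7 pairs
- [√57.7 × 0.1805 − 0.98] / 0.4663 = 0.839, so power = **79.9%**

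**Form B: p1 set from the odds ratio, p1 = p0ψ/[1 + p0(ψ − 1)].**

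- p1 = 0.477, t = 0.3993, n·t = 59.9 pairs
- [√59.9 × 0.1805 − 0.98] / 0.4663 = 0.894, so power = **81.4%**

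Simulating 200,000 studies under Form A gives 79.4% (score test), 79.0% (Wald) and 79.9% (likelihood ratio). Exact McNemar gives 75.9%.

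**Inverting the calculation.**

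| Quantity | Form A | Form B |
|---|---|---|
| Odds ratio at 80% power, 150 pairs | 2.13 | 2.10 |
| Odds ratio at 90% power, 150 pairs | 2.38 | 2.34 |
| Pairs for 80% power at 2.13 | 150.3 | 144.8 |
| Pairs for 90% power at 2.13 | 198.6 | 191.3 |
| Power at 2.0, 150 pairs | 72.3% | 73.8% |
| Pairs for 80% power at 2.0 | 179.6 | 173.5 |
| Power at 3.0, 150 pairs | 98.8% | 99.2% |

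**Can another reading give 90%?** Each of these departs from the text.

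- Correlation zero: t = 0.491, power 88.9%; the odds ratio at 90% is 2.16. The plan states 0.20.
- Unmatched comparison of two proportions: 88.7%. The plan states matched pairs.
- One-sided alpha: 88.0% to 89.1%. The plan states two-sided.
- 2.13 read as a marginal odds ratio: the within-pair odds ratio becomes 2.60 and power about 95%. With a continuity correction it is 92.0%, but that version's odds ratio at 90% is 2.08. The planned model does not estimate a marginal odds ratio.

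**The per-SD statement.** Using n = (1.96 + z_power)² / [P(1−P)·(ln OR)²] with P = 0.20, an odds ratio of 1.50 at 80% needs 298 subjects and 1.60 at 90% needs 297. These figures are therefore right for their stated inputs. Those inputs describe an unmatched sample with 20% PAF, whereas the study has 150 cases and 150 matched controls, and the correlation is zero here but 0.20 in the binary calculation. The consequence depends on the AHI distribution, which the plan does not give. Simulated conditional logistic regression with 150 pairs and correlation 0.20 gives about 85% to 86% power at 1.50 per SD if AHI is normal, and about 67% to 84% if it is lognormal with log-SD between 0.5 and 1.0. Both distributions are assumptions made for this check.

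**The case against.** The arithmetic has no good answer, but four points on weight and scope deserve a hearing.

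- **The cause is not known.** The 80% odds ratio in Form A matches the printed 2.13, which suggests that an 80% result was labelled 90%. In Form B it is 2.10, and leaving the correlation at zero comes within about a point of 90%. The documents do not show which slip occurred. This stands: what is established is that the figure does not follow from its inputs.
- **It is not the power of the primary SA1 model.** That model takes AHI as continuous, per unit. The AHI ≥ 15 calculation is an alternative, and the SA1 method text specifies no AHI ≥ 15 test. This limits the weight of the error but does not remove it, since the plan uses the figure to argue that SA1 is adequately powered.
- **Most of the cited range is well covered.** Power is about 99% at an odds ratio of 3. The sufficiency sentence fails only between 2.0 and about 2.1. This also stands.
- **The per-SD issue is separate and has no fixed direction.** Agreed. The mismatch of inputs is visible in the plan, but its numerical effect rests on assumed distributions. The main conclusion does not depend on it.

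**Conclusion.** The concern holds. With the stated control prevalence, correlation, number of pairs and alpha, power at an odds ratio of 2.13 is 79.9% to 81.4%, about 9 to 10 percentage points below the stated 90%. No reading consistent with the text restores 90%. The result rests on the plan's own inputs and on taking the odds ratio as the within-pair one that the planned model estimates; the range reflects the two ways of setting exposure in cases. Confidence is high for this binary figure. The per-SD figures are not arithmetically wrong, but their inputs do not describe the matched design, and how much that matters cannot be settled from the documents.

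**What to change.** In the SA1 power paragraphs of Sections 9 and 10:

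1. State that 150 matched pairs detect an odds ratio of 2.13 with 80% power and about 2.35 with 90% power (2.34 to 2.38, depending on how exposure in cases is set).
2. Limit the sufficiency sentence, for AHI ≥ 15, to odds ratios of about 2.1 and above, and say that power at 2.0 is about 72% to 74%.
3. Separately, recompute the per-SD figures for 150 pairs under conditional logistic regression, using the same correlation as the binary calculation and a stated AHI distribution. No replacement values are offered here, because the plan gives no distribution. The current figures are conservative if AHI is normal but may not be if it is right-skewed.

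The cost is rewording, one recalculation and a less favourable stated power for AHI ≥ 15. No participants are added and the analysis is unchanged.

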10. DATA ANALYSIS

EXPOSURES: *Primary:* 1) SDB defined by AHI, i.e. number of apneas + hypopneas/hour of sleep. *Secondary:* 1) Hypoxia: % sleep time with $\text{SaO}_2 < 90\%$, 2) Obstructive Sleep Apnea [obstructive apneas and hypopneas/hour of sleep, obstructive apnea hypopnea index (OAHI)], 3) Central Sleep Apnea [central apneas/hour of sleep, Central Apnea Index (CAI)], 4) Periodic Breathing and 5) EEG arousals [per hour of sleep, Arousal Index (AI)].

OUTCOME: 1) PAF (SA1) and 2) AF burden defined as frequency of AF paroxysms overall and based on self-reported sleep vs. wake (SA2 and 3)

COVARIATES: Age, race, body mass index (BMI, kg/m^2), waist circumference (cm), anti-arrhythmic/beta blocker/calcium channel blocker/ACE inhibitor/angiotensin receptor blocker medications, pacemaker, defibrillator, heart failure (NYHA class), BP, diabetes mellitus, left atrial volume, LVEF, caffeine use, alcohol use and smoking (current versus never smoker or pack years) and activity level. When assessing hypoxia as the relevant exposure, pulmonary disorders will be included as potential confounders.

Table 2. Mediator (SA1) or Outcome (SA3)

Domain	Primary	Secondary	Rationale
Echocardiographic Measures	Left Atrial Volume (ml/m^2)	LA Pressure, LA Systolic Strain, RA area, RA Pressure, LAA Peak Anterograde Flow Velocity (cm/s), Right Atrial Pressure (mmHg), LVEF, LVMI, LVH (concentric LVMI >0.41 , eccentric ≤ 0.41).	Left Atrial Volume predicts risk of AF and PAF ¹⁰³⁻¹⁰⁶ . Secondary measures also associated with AF.
Autonomic Function (Heart Rate Variability)	SDNN (ms) (Time Domain HRV Measure)	Time Domain (r-MSSD (ms), pNN50), Frequency Domain [LF (Hz), HF (Hz), LF/HF], Graphical Parameters (HR patterns, power spectral analysis, Poincaré plots and beat-by-beat HR tachograms) and Novel non-linear measures (e.g. Conditional Entropy ¹⁰⁷).	Reduced SDNN and LF/HF have been identified as AF triggers ⁴⁰ .
Systemic Inflammation	hs-CRP (mg/L)	IL-6 (pg/ml), sIL-6R (ng/mL)	hs-CRP and IL-6 associated with SDB and AF ⁴⁷⁻⁴⁹ . s-IL6R varies with overnight hypoxia ⁴⁶
Oxidative Stress	Endothelin-1 (pg/ml)	Urinary isoprostane 8-epi-prostaglandin F2a (ng/ mmolCr), Oxidized LDL (U/L)	Endothelin-1 implicated in AF ⁵⁷⁻⁵⁹ . Isoprostane ⁶⁰⁻⁶² and oxidized LDL sensitive to SDB ⁷⁶ .

ANALYTIC METHOD BY AIM.

SA 1. Quantify the extent that SDB and its subtypes are associated with PAF. This aim will be addressed by fitting conditional logistic regression models that condition on the matched pair. We will separately analyze each SDB variable (primary variable: AHI) to obtain an estimate and 95% CI of the odds ratio of PAF for a 1-unit increase in the SDB exposure. Non-linear effects between SDB and the log odds of PAF will be assessed using restricted cubic splines. Knots for the spline will be based on the SDB threshold at which PAF risk increases. Unadjusted and hierarchical adjusted models will be performed using the covariates listed above.

The secondary exposure variables (e.g. hypoxia, OAHI, CAI, AI) will be considered in separate models.

Exploratory Aim 1a. Cardiac structure, autonomic and biochemical variables (Table 2) will explain a proportion of the SDB and PAF relationship. This aim will be addressed by applying Pearl's mediation formula ¹⁰⁸ to the conditional logistical regression model. This approach will allow a causally sound definition of the mediation effect of a given intermediate variable in the relationship between SDB (defined by AHI) and PAF. The approach involves a model for each mediator (e.g. a general linear model for a continuous mediator) and possibly a random effect to account for clustering due to matching and can be thought of as a generalized structural equations model. This approach will allow us to simultaneously assess multiple mediators and will also allow us to consider AHI as a continuous variable. Each model will be fit using likelihood methods and model fit will be checked using appropriate information criteria. After fitting the overall model, we will obtain, for each mediator, an estimate of the indirect effect (e.g. the portion of the overall effect of SDB on PAF mediated through the intermediate variable). A bootstrap resampling technique will be used to obtain a 95% CI for each indirect effect. If the CI does not contain zero, this will indicate statistically significant mediation.

Exploratory Aim 1b. Explore age interactions in the SDB-PAF relationship. Each conditional logistic regression model will include an interaction between age and SDB to investigate if age is a modifier of the effect of SDB on PAF, i.e. whether the odds ratio of PAF for a 1-unit increase in SDB varies by age.

SA2. Examine patterns of PAF burden via 7-21 day continuous ECG monitoring relative to SDB. We will model the relationship between mean frequency AF paroxysm variation and SDB (e.g. AHI considered as a continuous variable). A linear regression model will be used to assess possible quadratic and threshold effects of SDB on variation. These models may also include sleep state by SDB interaction terms (along with the state indicator) to examine if the effect of SDB on variation differs by sleep state. Maximum likelihood (based on a normal distribution for variation if appropriate) will be used to fit models, and the Akaike Information Criterion (AIC) will be used to select the best fitting model. Estimates of the effect of SDB on variation (and corresponding 95% CI) will be obtained based on the selected model.

SA3. Examine the effects of SDB (AHI \geq 15) treatment for 3 months on AF paroxysm frequency and also measures of autonomic function, cardiac morphology, biochemical measures in those with SDB and PAF. For this subgroup of SDB (AHI \geq 15) and PAF, we will perform paired t-tests to compare pre- and post-treatment mean outcomes (Primary outcome: AF paroxysm frequency from 1-week ECG monitoring) and also ECHO and biochemical measures. For any outcome for which a departure in normality is found (based on the Shapiro-Wilk test) but a transformation of the outcome cannot be found to adequately address the issue, we will use the Wilcoxon signed rank sum test to detect a difference in the distribution of the pre- and post- responses. This assessment is not intended to be confirmatory, but rather to provide estimates of variability and effect sizes to inform future studies/randomized trials. Linear regression models will then be developed to model PAF burden at the 3 month visit by conditioning on baseline PAF burden, baseline SDB,

and time from baseline to 3 month visit. Additional adjusted models will carefully consider the covariates list above.

POWER BY AIM.

SA 1. A sample size of 300 will be able to detect an odds ratio of 1.50 with 80% power (and 1.60 with 90% power), assuming a 2-sided alpha level of 0.05, a correlation in AHI between cases and controls of zero and a probability of PAF of 0.20 when AHI is set at its mean value. Note that the odds ratio is interpreted as the odds ratio for PAF for a 1 standard deviation increase in AHI. Alternatively assuming that the probability that $AHI \geq 15$ for patients without PAF is 30% ⁶⁴, a sample size of 150 matched pairs will be able to detect an odds ratio of PAF of 2.13 with 90% power assuming a 2-sided alpha-level of 0.05. Note that this calculation assumes that the correlation for SDB between subjects with and without PAF is 0.20, as suggested by Dupont (1988)¹⁰⁹ when the correlation is unknown. Our prior cross-sectional work demonstrating SDB-AF odds ratio point estimates of 2-4 ^{1,2} supports sufficient power to address this aim.

Exploratory Sub-Aim 1a. To calculate the power to detect mediation, a difference in coefficients approach will be used ¹¹⁰ which involves the fitting of two logistic regression models that model the association between SDB ($AHI \geq 15$) and the log odds of PAF (one with and the other without the potential mediator in the model) to estimate the proportion of exposure effect that is mediated. Assuming a correlation between the adjusted and unadjusted effect estimates of 0.9 and that the probability of PAF in SDB and no SDB is 0.07 and 0.01 respectively (based upon prior data ²), a sample size of 150/group will be able to detect mediation proportions of 0.5 with 84% power assuming a 2-sided 0.05 alpha-level test. Although power may be reduced depending on the observed imbalance in sample sizes for the SDB and no SDB groups, power will be increased due to matching (not taken into account here to be conservative).

SA2. Using a two-sample t-test (2-sided 0.05 alpha-level) to test for a difference in mean variation between the SDB ($AHI \geq 15$) and no SDB groups, a sample size of 150 (75 with SDB and 75 without SDB) will detect mean differences within 0.46 standard deviations with 80% power and 0.53 standard deviations with 90% power.

SA3. For a log-normally distributed outcome, assuming a correlation between pre- and post-PAF burden of 0.8 and a coefficient of variation of 1.5 (based upon prior data ¹¹¹), a sample size of 75 will detect a mean ratio between post and pre PAF burden of 0.83 with 83.1% power based on a paired t-test and a two-sided significance level of 0.05.

